8.2. Sample Description

Continuous data will be described using means, standard deviations, and confidence intervals, while categorical data will be described using counts/percentages.

8.3. Aim-Specific Plans

Plans for Aim 1 (PRIMARY).

Treatment response will be calculated as the depression (HDRS) scores from pre- to post-treatment. A two-way analysis of variance (ANOVA) will be performed using within-participant factor of time (before or after treatment), between-participant factor stimulation type (delta-beta tACS, active-sham), and the interaction between time and stimulation type. We hypothesize to find an interaction between time and stimulation type. Post hoc differences will be investigated. We hypothesize that the predicted interaction will be driven by a decrease in depressive symptoms for delta-beta tACS compared to the active-sham. Sensitivity analyses will be conducted to evaluate the specificity of these effects: a similar analysis with anxiety symptoms as the dependent variable and we do not expect that delta-beta tACS will have any effect on anxiety symptoms.

Further, we will conduct exploratory generalized linear mixed models will be conducted to examine potential confounds on treatment effect (e.g., age, sex, baseline depressive symptoms).

Plans for Aim 2 (SECONDARY).

Delta-beta phase amplitude coupling will be calculated between the phase of delta oscillations (2-3 Hz) in prefrontal electrodes (FCz and surrounding electrodes) and the amplitude of beta oscillations (15- 25 Hz) in left motor electrodes (C3 and surrounding electrodes). The instantaneous phase and amplitude of these oscillations will be calculated by averaging the signal in these two regions of interest, band-filtering the signal to the specified range, and then performing the Hilbert transform on the signal. Phase-amplitude coupling (PAC) is then calculated by creating a hybrid signal using the amplitude of beta oscillations in left motor electrodes and the phase of delta oscillations in prefrontal electrodes:

[†][1] www.consort-statement.org , [2] www.strobe-statement.org, [3] www.icmje.org

^[4] Wasserstein RL, et al. (2016), The ASA's Statement on p-Values, *The American Statistician*, 70:2, 129-133.

^[5] Wasserstein RL, et al. (2019), Moving to a World Beyond p < 0.05, *The American Statistician*, 73:sup1, 1-19.

^[6] Amrhein, et al. (2019), Scientists rise up against statistical significance, *Nature* 567, 305-307.

^[7] Editorial (2019) It's time to talk about ditching statistical significance: ... *Nature* 567, 283-283.

$$PAC = \left| \frac{\sum_{t=1}^{N} M * e^{i\theta}}{N} \right|$$

 $PAC = \left| \frac{\sum_{t=1}^{N} M * e^{i\theta}}{N} \right|$ M is magnitude of beta oscillations, θ is angle of delta oscillations, N is number of time points

The PAC value is normalized by creating a null distribution by randomly shifting the beta timeseries by at least 10% of the number of time points. Then, PAC is calculated between the delta-phase timeseries and each of these randomly shifted beta-amplitude timeseries. Finally, PACZ is calculated as the z-transformed true PAC value relative to the null distribution.

A two-way analysis of variance (ANOVA) will be performed using within-participant factor of time (before or after treatment) and between-participant factor stimulation type (delta-beta tACS, active-sham). We hypothesize to find an interaction between time and stimulation type. Post hoc differences will be investigated. We hypothesize that the predicted interaction will be driven by an increase in delta-beta coupling for delta-beta tACS compared to the active-sham. Sensitivity analyses will be conducted to evaluate the specificity of these effects: a similar analysis with theta-gamma coupling as the dependent variable and we do not expect that delta-beta tACS will have any effect on theta-gamma coupling.

Further, we will conduct exploratory generalized linear mixed models will be conducted to examine potential confounds on treatment effect (e.g., age, sex, baseline depressive symptoms).

Plans for Aim 3 (SECONDARY).

Goal-directed behavior will be calculated as the average decision to perform the HARD task across blocks. A two-way analysis of variance (ANOVA) will be performed using within-participant factor of time (before or after treatment) and between-participant factor stimulation type (delta-beta tACS, active-sham). We hypothesize to find an interaction between time and stimulation type. Post hoc differences will be investigated. We hypothesize that the predicted interaction will be driven by an increase in goal-directed behavior for delta-beta tACS compared to the active-sham. Sensitivity analyses will be conducted to evaluate the specificity of these effects: a similar analysis with reward-evaluation as the dependent variable and we do not expect that delta-beta tACS will have any effect on rewardevaluation.

Further, we will conduct exploratory generalized linear mixed models will be conducted to examine potential confounds on treatment effect (e.g., age, sex, baseline depressive symptoms).

Plans for Aim 4 (EXPLORATORY).

Exploratory analyses are planned only if effects are seen on depressive symptoms (Aim 1). If so, we plan to explore the potential effects specific to anhedonia symptoms. Treatment response will be calculated as the change in anhedonia (SHAPS-C) scores from pre- to post-treatment. A two-way analysis of variance (ANOVA) will be performed using within-participant factor of time (before or after treatment) and between-participant factor stimulation type (delta-beta tACS, active-sham). We hypothesize to find an interaction between time and stimulation type. Post hoc differences will be investigated. We hypothesize that the predicted interaction will be driven by a decrease in anhedonia symptoms for delta-beta tACS compared to the active-sham.

Further, we will conduct exploratory generalized linear mixed models will be conducted to examine potential confounds on treatment effect (e.g., age, sex, baseline non-anhedonic depressive symptoms).

Exploratory analyses with anhedonia symptoms will not be conducted if effects for overall depressive symptoms (Aim 1) are not found.

Planned Interim Analyses

No interim analyses will be performed.

The experiment proposed here will utilize a parallel arm design, and primary analyses will use a repeated-measures ANOVA with one within-participant factor (before and after treatment) and one between-participants factor (deltabeta, placebo). With an average effect size of 0.286 partial-eta square estimated from existing literature on single session BA, we estimate that we need at least 15 participants per group to achieve 80% statistical power. Using a conservative estimate of 0.5 correlation between estimates, we still reach ~99% power with 40 participants (Figure 3). Data will be collected until we reach 40 participants. Given the similarity in stimulation methodology between the current experiment and our previous experiment (Riddle et al., 2021), we anticipate adequate levels of power for hypothesis testing with 40 participants. Moreover, other studies of combined psychotherapy and stimulation have reported similar sample sizes (Neacsiu et al., 2022).

[figure not shown]

Figure 3. Power analysis for impact of BA + tACS on depressive symptoms with ANOVA.

10. Data Capture and Database Management

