	Aim 4 (EXPLORATORY). Explore the effects of delta-beta transcranial alternating current stimulation (tACS) on anhedonia symptom severity from pre- to post-treatment.				
Target Population	Inclusion Criteria We will recruit individuals 18 years and older who meet criteria for current major depressive disorder (MDD) as captured by the Mini International Neuropsychiatric Interview (MINI). Participants will be recruited from the Chapel Hill and Durham areas.				
	 Exclusion Criteria Participants must not have active suicide intent as determined by the Columbia Suicide Severity Rating Scale (C-SSRS). Active suicide intent will be captured in responses to items 4 and/or 5 on the C-SSRS. Participants must not meet criteria for current severe substance use disorder, anorexia nervosa, or active psychosis as captured by the MINI. Participants may not currently be in psychotherapy and have not received any other psychotherapy and/or stimulation (ECT, TMS) within the last 4 weeks. 				

	 Any participants taking psychotropic medication must be on a stable dose for at least 4 weeks with no planned dose changes within the next 4 weeks. (for female participants) Participants must not be pregnant or breastfeeding. Participants may not have any medical or neurological illness for which symptom presentation or treatment could interfere with study participation Participants may not have undergone prior brain surgery Participants may not have any brain devices/implants, including cochlear implants and aneurysm clips Participants may not have had brain injury or concussion within the last three months Participants may not have a history of brain injury requiring current treatment
Numbers of Enrollees	Our target sample size is N = 40. 20 participants will be assigned to the BA + delta-beta tACS condition and 20 will be assigned to the BA + active sham condition. We conservatively estimate to enroll 80 participants as a ceiling for the sake of IRB approval.
	We anticipate that at least n = 30 of the enrollees will complete all aspects of the protocol and have complete data.
Interventions or Exposures/Conditions	Single-session BA: Participants will take part in a 90-minute BA intervention tailored to treat depression. This intervention will include psychoeducation, activity monitoring, evaluation of values, and activity planning and scheduling.

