	Neurostimulation: We will use the DC-STIMULATOR MC Stimulator Plus for investigational purposes to deliver either cross-frequency delta-beta or active sham transcranial alternating current stimulation. Active sham treatment will include 20 seconds of ramp in to 40 seconds of tACS with a ramp out of 20 seconds for a total of 80 seconds of stimulation.
Outcome Measures	For Aim 1 (PRIMARY). Change in clinician-rated depressive symptoms using HDRS between baseline visit and 2-week follow-up visit.
	For Aim 2 (SECONDARY). Phase-amplitude coupling between delta-beta oscillations during task performance of the Streamlined Expenditure of Effort for Reward Task (S-EEfRT) at baseline visit and 2-week follow-up visit.
	For Aim 3 (SECONDARY). Behavioral metric, percentage of hard trials chosen, during the S-EEfRT at baseline visit and 2-week follow-up visit.
	For Aim 4 (EXPLORATORY). Change in clinician-rated anhedonia symptoms using SHAPS-C between baseline visit and 2-week follow-up visit.

PTOLOCOL NUMBER \#>	15 September 2022
Statistical Analysis Plans for Each Aim	Aim 1 Plans. Repeated-measures ANOVA with one within-participant factor (before and after treatment) and one between-participants factor (delta-beta, sham) comparing change in clinician-assessed depressive symptoms. Aim 2 Plans. Repeated-measures ANOVA with one within-participant factor (before and after treatment) and one between-participants factor (delta-beta, sham) comparing change in delta-beta coupling. Aim 3 Plans. Repeated-measures ANOVA with one within-participant factor (before and after treatment) and one between-participants factor (delta-beta, sham) comparing change in goal-directed behavior. Aim 4 Plans. Repeated-measures ANOVA with one within-participant factor (before and after treatment) and one between-participants factor (delta-beta, sham) comparing change in clinician-assessed anhedonia symptoms.
Study Duration	1 year

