8.1. Strategies that Apply to all the Aims

All testing described below assumes a significance threshold of p = 0.05. Analyses will be deemed to be statistically significant if the p-value is less than this threshold. An analysis that does not exceed this threshold will be considered inconclusive.

There may be additional covariates included in the analysis. Data will be assessed for normality and, if deemed necessary, corrective procedures will be applied (e.g., log normalization). Based on our previous dataset, we expect that the variables used here will be approximately Gaussian. However, if the distribution of a variable displays a skewed tail and a test for normality fails, then it is justified to use a corrective procedure. This correction will be applied upon consideration of the variables themselves, and not based on the result of the intended analysis.

Human studies are prone to drop-out, missing data, and interval-censored values. The reasons for drop outs, missing / censored data values, and protocol departures will be documented in the database. Best practices for dealing with incomplete data will depend on the documented causes of those occurrences.

The analysis plans will include outcome-dependent exploratory analyses to generate new hypotheses.

To help ensure replicability of the research, the analysis plans will be reviewed and finalized prior to collection of data (*a priori*). For each specific aim, the analysis plans specify detailed steps for obtaining estimates of the population parameters of interest (e.g., treatment effects) and for making inferences.

- Human studies are prone to drop-out, missing data, and interval-censored values. The reasons for drop-outs, missing / censored data values, and protocol departures will be documented in the database. Best practices for dealing with incomplete data will depend on the documented causes of those occurrences. In the analysis plans established a priori, the strategies for coping with incomplete data will be based on anticipated causes. Alternative methods for dealing with incomplete data will play important roles in the sensitivity analyses.
- All hypothesis tests yielding large p-values will be reported as being inconclusive. For all sample sizes, all hypothesis test procedures are (by design) incapable of establishing that the null hypothesis is true.

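### The primary HDRS analysis leaves out the baseline score already collected; a prespecified ANCOVA would cut variance by about 23% at N = 40 if the pre-post correlation is 0.5 and the SDs are equal

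*Combined protocol and SAP*

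**What the plan says.** Section 8.3 sets the primary Aim 1 analysis: "A two-way analysis of variance (ANOVA) will be performed using within-participant factor of time (before or after treatment), between-participant factor stimulation type", plus their interaction, with HDRS as the outcome. The synopsis agrees ("Aim 1 Plans. Repeated-measures ANOVA with one within-participant factor (before and after treatment"), as do Table 1 and the sample-size rationale (section 9 in the table of contents).

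Table 2 and section 7.2 show HDRS taken at the baseline visit and at the 2-week visit. Baseline severity is mentioned in section 8.3 only for exploratory generalized linear mixed models that will "examine potential confounds on treatment effect (e.g., age, sex, baseline depressive symptoms". The terms of those models are not stated.

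Section 8.1 adds, for all aims, "There may be additional covariates included in the analysis", without naming any. The same section says that "the analysis plans will be reviewed and finalized prior to collection of data".

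The power paragraph uses two figures: "With an average effect size of 0.286 partial-eta square estimated from existing literature on single session BA", and "Using a conservative estimate of 0.5 correlation between estimates". The synopsis gives the expected number of completers: "We anticipate that at least n = 30 of the enrollees will complete all aspects of the protocol and have complete data".

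**The concern.** A change score fixes the slope of follow-up on baseline at 1. ANCOVA estimates that slope from the data. Under randomization both target the same arm difference, and in large samples ANCOVA is never less precise. With 20 per arm and no stratification (section 5.5), it also removes the influence of a chance baseline imbalance on the estimate.

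The exploratory mixed models do not clearly fill the gap. With complete data, adding baseline as a main effect leaves the time-by-stimulation estimate unchanged. The estimate becomes baseline-adjusted only if the model has a baseline-by-time term, and none is mentioned. The open-ended covariate sentence in section 8.1 commits the primary model to nothing, so which adjusted estimate would count, if any, is undecided.

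What is at stake is precision. The planned test keeps its type I error rate.

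**Working it through.** **Inputs from the documents.** Partial eta squared 0.286; correlation 0.5, read as the pre-post HDRS correlation; 40 participants, 20 per arm; at least 30 completers; significance threshold 0.05 (taken as two-sided).

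**Assumption.** The documents give no HDRS SD. Let k be the post SD divided by the pre SD; the base case is k = 1.

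**1. The plan's power figure.** f² = 0.286/0.714 = 0.4006, so f = 0.633 and the standardized difference is 2f = 1.266. Noncentrality f² × N gives power 97.4% at N = 40. The repeated-measures between-factor formula at correlation 0.5 gives 99.5%, and the within-between formula gives at least 99.98%. The stated figure of about 99% is therefore broadly reproduced.

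**2. Variance per participant, k = 1** (in units of the HDRS variance).
- Change score: 2(1 − ρ) = 2 × 0.5 = 1.00.
- ANCOVA: 1 − ρ² = 0.75.
- Large-sample ratio: (1 + ρ)/2 = 0.75, a 25% reduction.
- Cost of estimating the slope: multiply by 1 + 1/(N − 4), which is 1.028 at N = 40 and 1.038 at N = 30.
- Result: 0.771 at N = 40 (22.9% reduction) and 0.779 at N = 30 (22.1%).

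A simulation of 100,000 trials at 20 per arm gave 23.0%. The gain equals a change-score analysis of about 40/0.771 = 52 participants.

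**3. Power and detectable difference** (noncentral t, ρ = 0.5, k = 1; the SD of change then equals the SD of the score).

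| Quantity | N | Change score | ANCOVA |
|---|---|---|---|
| Detectable difference at 80% power | 40 | 0.91 SD | 0.80 SD |
| Detectable difference at 80% power | 30 | 1.06 SD | 0.94 SD |
| Power at 0.8 SD (illustrative, not in the documents) | 40 | 69% | 80% |
| Power at 0.8 SD (illustrative, not in the documents) | 30 | 56% | 67% |
| Power at the plan's effect, 1.27 SD | 40 | 97.4% | 99.3% |
| Power at the plan's effect, 1.27 SD | 30 | 91.7% | 96.6% |

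In 20,000 simulated trials at 20 per arm, type I error was 0.052 for the change score and 0.048 for ANCOVA, so both tests are valid.

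**4. Sensitivity.** The general large-sample ratio is k²(1 − ρ²)/(1 + k² − 2ρk), multiplied by 1.028 at N = 40.

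| ρ | k | Large-sample ratio | Ratio at N = 40 | Variance under ANCOVA |
|---|---|---|---|---|
| 0.3 | 1 | 0.650 | 0.668 | 33% lower |
| 0.5 | 1 | 0.750 | 0.771 | 23% lower |
| 0.7 | 1 | 0.850 | 0.874 | 13% lower |
| 0.8 | 1 | 0.900 | 0.925 | 7.5% lower |
| 0.5 | 0.8 | 0.571 | 0.587 | 41% lower |
| 0.5 | 1.25 | 0.893 | 0.918 | 8% lower |
| 0.5 | 1.5 | 0.964 | 0.991 | 1% lower |
| 0.6 | 1.25 | 0.941 | 0.967 | 3% lower |
| 0.7 | 1.25 | 0.981 | 1.008 | 1% higher |
| 0.8 | 1.25 | 1.000 | 1.028 | 3% higher |

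The large-sample ratio never exceeds 1, so the loss at N = 40 is bounded by the slope cost of about 2.8%.

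**5. Chance imbalance.** The SD of the baseline arm difference is √(2/20) = 0.316 SD, so a difference above 0.5 SD in either direction has probability 11%. At ρ = 0.5 and k = 1, a 0.5 SD imbalance moves the change-score estimate by (1 − 0.5) × 0.5 = 0.25 SD in that trial. The standard error already allows for this; it is not a bias over repeated trials.

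**6. Mixed models.** In three simulated complete datasets, a mixed model with covariates as main effects gave exactly the change-score estimates (−2.7725, −4.5667, −5.1119). Adding baseline by time gave exactly the ANCOVA estimates (−2.9041, −4.3487, −4.6698).

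**The case against.** The strongest reply is that 23% is a favourable reading. The plan calls 0.5 conservative. For a test on change, that implies the planners expect a higher correlation, and ANCOVA gains less as the correlation rises. Entry requires current MDD, which may narrow the baseline spread while nothing narrows the 2-week score, so a post SD above the pre SD is plausible. Where both hold, the gain can disappear, as the last rows of the sensitivity table show. This stands: the 23% is conditional, and the full range includes no gain and a slight loss. The loss is capped at about 2.8% at N = 40, while the possible gain is much larger.

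A second reply is that power is already near 99%. At the plan's effect size the benefit is indeed small. But that effect comes from the literature on single-session BA, and both arms here receive BA (section 4.2). The tested contrast is tACS against sham, for which the documents give no effect size. If that contrast is smaller, precision matters more.

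A third reply is that nothing about the primary analysis is open, because the plan names the unadjusted ANOVA as primary and calls the covariate models exploratory. That is largely fair. What stays open is the optional-covariate sentence in section 8.1 and the form of the exploratory models.

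Finally, the gain for delta-beta coupling, hard-task choices and SHAPS-C cannot be quantified from the documents. That is correct; extending the model to them rests on the general argument and on consistency.

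**Conclusion.** The point holds as a nearly free improvement. The planned ANOVA is valid, but it leaves out a baseline measurement the trial already takes. At a correlation of 0.5 with equal SDs, prespecified ANCOVA lowers the variance by 22.9% with 40 analysed and 22.1% with 30, and the standard error by about 12% at N = 40. This rests on reading the plan's 0.5 as the pre-post HDRS correlation and on equal SDs, which the documents neither support nor contradict. Confidence in the size of the gain is therefore medium; confidence that adjustment costs almost nothing is high.

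**What to change.** In section 8.3, prespecify as the primary Aim 1 analysis a linear model of 2-week HDRS on stimulation arm and baseline HDRS, reporting the adjusted arm difference with a 95% confidence interval. Modelling HDRS change with the same covariate gives the identical arm estimate, so the stated outcome can stay as it is. Keep the 2 × 2 ANOVA as supportive.

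Use the same form for normalized delta-beta coupling, percentage of hard choices and SHAPS-C, each with its own baseline. For the exploratory covariate analysis, add age and sex to this model. If mixed models are kept, state their terms, including baseline by time.

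Align the synopsis, Table 1 and the sample-size text. The cost is wording and one degree of freedom. No new data are needed, since a baseline value is already collected for every outcome. Make the change before data collection, as section 8.1 requires of the analysis plans.

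### The delta-beta coupling score keeps an offset that its time-shift null cannot remove; where that offset is large and unfavourably angled, PACZ can stay flat or fall as coupling rises

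*Combined protocol and SAP*

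**What the plan says.** Aim 2 is numbered here as in Section 8.3, where it is the coupling outcome (Section 3 lists coupling as Aim 3).

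The delta band is 2-3 Hz and the beta band 15-25 Hz, both processed with the Hilbert transform. The coupling value comes from "creating a hybrid signal using the amplitude of beta oscillations in left motor electrodes and the phase of delta oscillations in prefrontal electrodes". In symbols it is PAC = |Σ M e^{iθ} / N|, where "M is magnitude of beta oscillations" and θ is the delta angle. No centring of M and no correction for uneven delta phase is stated.

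The null is made by "randomly shifting the beta timeseries by at least 10% of the number of time points". The delta series stays as recorded, and the coupling value is recomputed for every shifted copy. The score that enters the ANOVA is a z-value: "PACZ is calculated as the z-transformed true PAC value relative to the null distribution". The hypothesis is that the time-by-arm interaction will be "driven by an increase in delta-beta coupling for delta-beta tACS compared to the active-sham".

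The plan does not say whether PAC is computed on the continuous recording or on event-locked epochs. It gives no record length, number of trials, expected coupling or power for this outcome.

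**The concern.** The Aim 2 hypothesis needs a score that goes up when coupling goes up. A score built from uncentred magnitude need not do so. Part of the vector whose length is taken has nothing to do with coupling: it is mean beta magnitude multiplied by the unevenness of delta phase over the analysed samples. Because the length is taken before z-scoring, the null subtracts a number and leaves that vector in place. Two people with the same coupling can then get different PACZ values, and a real increase can be scored as no change or as a fall.

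At stake is the sensitivity of a secondary test with 20 per arm. The theta-gamma specificity check is described as a similar analysis, so it presumably inherits the same property, and a null result there would be harder to read.

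**Working it through.** **The plan's own figure.** The only power statement is about 99% with 40 participants, for depressive symptoms. From partial eta-squared 0.286, f² = 0.286/0.714 = 0.4006. With correlation 0.5, λ = 0.4006 × 40 × 2/(1 + 0.5) = 21.4 on (1, 38) df, giving power 0.994. It reproduces, but it says nothing about PACZ.

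**Step 1, identity.** mean(M e^{iθ}) = mean(M) × mean(e^{iθ}) + mean[(M − mean M) e^{iθ}]. Call the first term the offset B and the second the coupling vector C (plus noise). A shift of the beta series that wraps around, which I assume, changes neither mean(M) nor θ. B is therefore identical in the observed value and in every surrogate, and PACZ compares |B + C + noise| with |B + noise|.

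**Step 2, worked example.** Assumed values, in units of mean beta magnitude: |B| = 0.03, |C| = 0.05 (10% modulation depth), noise 0.0104 per axis.

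- Uncentred null: mean ≈ 0.03 + 0.0104²/(2 × 0.03) ≈ 0.032, SD ≈ 0.010.
- Observed length before noise: 0.03 + 0.05 = 0.08 if aligned, √(0.03² + 0.05²) = 0.058 at 90 degrees, 0.05 − 0.03 = 0.02 if opposed.
- Mean PACZ, allowing for noise in the observed value: 4.9, 2.7 and −0.9.
- Centred: null mean 0.0104 × √(π/2) = 0.0130, SD 0.0104 × √(2 − π/2) = 0.0068. PACZ is 5.6 at every angle.

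With opposed phase and |C| of 0, 0.01, 0.02 and 0.03, uncentred PACZ is 0, −0.89, −1.60 and −1.88; centred it is 0, 0.42, 1.46 and 2.77. Uncentred PACZ does not return to zero until |C| = 0.06, twice the offset. With no coupling both are zero.

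**Step 3, how large the offset might be.** What matters is b = |B| divided by noise per axis. In the example b = 0.03/0.0104 = 2.9. Simulated 1/f records filtered to the plan's bands give:

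- Continuous, 1-20 minutes, no phase locking: b about 0.4-0.5. At 10 minutes the phase unevenness is about 0.0018, against 0.03 in the example.
- 120 epochs of 0.4-2 s, no phase locking: b about 0.6-1.0.
- Phase-locked epochs (peak inter-trial coherence about 0.4-0.9): b about 0.7-16, smallest when the window spans whole delta cycles.

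**Step 4, power.** Noise model, change-score t-test (equivalent to the time-by-arm interaction), 20 per arm, two-sided 5%, coupling assumed to rise from 2 to 3.4 noise SD in the active arm only:

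| b | Random angle | Aligned |
|---|---|---|
| 0 (centred) | 0.82 | 0.84 |
| 0.3 | 0.81 | 0.84 |
| 1 | 0.78 | 0.84 |
| 2 | 0.59 | 0.86 |
| 3 | 0.37 | 0.85 |
| 5 | 0.13 | 0.86 |

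A separate run of this kind of model gave about 0.85 centred, 0.67 at b = 2 and 0.39 at b = 3 with random angles, so these figures carry several points of uncertainty. With opposed phase, power is 0.01 at b = 3; at b = 5 it is 0.00, and the test is significant in the wrong direction 73% of the time. Across the coupling sizes tried, the random-angle loss is 0-3 points at b = 0.3 and 2-14 points at b = 1.

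At weak coupling (0.5 to 1.7 SD) with an aligned offset of 0.5 SD, uncentred magnitude does better: 0.67 against 0.52-0.54.

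**Step 5, signal-level check.** Mean PACZ with opposed phase, at beta modulation of 0, 3, 6 and 10%:

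| Data | Uncentred | Centred |
|---|---|---|
| Continuous, no phase locking | −0.2, 2.8, 7.7, 13.9 | −0.2, 3.7, 8.9, 15.4 |
| 1 s epochs, coherence about 0.4 | 0.0, −1.6, −2.5, −1.6 | −0.2, 1.1, 3.2, 6.1 |

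On continuous data PACZ still rises. On phase-locked short epochs it falls below zero.

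**The case against.** The algebra is not in dispute; the size is. The documents give no epoch length, trial count, recording length, evoked delta or preferred phase. Shifting a series by at least a tenth of its points fits one long record at least as well as short windows. For such a record the offset is under half a noise SD. A 10-minute continuous simulation of a small coupling rise gave a standardised arm difference of 0.68 uncentred against 0.76 centred (gap 0.085, 95% interval 0.04-0.13): real but modest.

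Random angles are also an assumption. Section 4 describes a waveform that mimics the endogenous pattern, with the fast component centred at 90 degrees of each slow cycle. That suggests a shared preferred phase, whose angle to the offset is unknown and could be harmless or harmful.

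A reader might infer that any uneven delta phase costs Aim 2 power, or that the score manufactures a stimulation effect. The documents support neither. Power can be unchanged or higher when the offset is aligned, and with no coupling mean PACZ stays near zero whatever the offset. Section 8.1 also treats large p-values as inconclusive, which limits the harm from an attenuated result.

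All of this stands. It makes the loss conditional; it does not make PACZ track coupling as the hypothesis requires. Coupling is measured during task performance, and nothing excludes event-locked epochs, where the offset can be large.

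**Conclusion.** The point holds in conditional form. It is certain, given wrap-around shifts, that the offset survives the null and that PACZ depends on its angle to the coupling phase. If the offset is about 2 noise SD or more and the angle is random or opposed, PACZ can stay flat or fall as coupling rises, and power can drop substantially. If the data are long and continuous without phase locking, the loss is small. If the offset is aligned there is no loss, and at weak coupling there can be a gain.

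Which case applies cannot be read from the documents, so every magnitude rests on assumed recordings, coupling sizes and angles. Aim 2 is secondary, and the primary HDRS analysis is untouched. This is a worthwhile low-cost correction, not a threat to the trial's validity.

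**What to change.** Before unblinding, in Section 8.3 Aim 2, define PAC = |Σ (M − mean(M)) e^{iθ} / N|, with the mean taken over the same time points, and apply it to the observed series and to every shifted series. This is equivalent to subtracting mean(e^{iθ}) from each phase vector. Use the same definition for theta-gamma coupling. State whether PAC is computed on continuous or epoched data and, if epoched, the window. Leave the rest of the PACZ procedure as it is.

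The cost is one line of code and a sentence or two in the plan, with no new data. There are two downsides. Values will not be directly comparable with earlier PACZ results unless those are recomputed, which matters because earlier delta-beta findings are part of the rationale. Some power may also be given up if the offset happens to be aligned and coupling is weak.
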